- Aim 3a: The Shed-MEDS intervention will not result in significant reductions in quality of life, as measured by Behavioral and Psychological Symptoms of Dementia (BPSD) events and DEMQOL-proxy scores at the end of 90 days.

**Potential for Impact:** The data from this study will inform feasibility and the implementation barriers and facilitators specific to PWD, their family proxies, and dementia care ALF staff. This information will inform tailored adaptations to the Shed-MEDS intervention in preparation for a multi-center R01 trial to test the clinical effectiveness of deprescribing among PWD in ALF care settings.

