### **Primary Outcomes - Medications**

Total number of Medications: The primary data source is the resident's ALF medication administration record (MAR). We include both prescription and over-the-counter medications (OTC) (vitamins, herbal supplements also included) administered by the following routes: oral, intravenous, intramuscular and ophthalmologic medications. All surrogates receive a baseline structured interview with specific prompts for OTC medications they may be providing directly (and not administered by the facility).

PIMs are defined by previously published lists including the recently updated Beers criteria, the STOPP criteria, as well as the RASP list, for which there is a large degree of overlap. The total number of PIMs is the sum of medications that are found on any of these explicit lists.

Drug Burden Index (DBI): A DBI score is calculated separately for anticholinergic (DBIAC) and sedative medications (DBIs), which have been strongly linked to functional impairment, falls, and delirium. The drug burden is the sum of each individual anticholinergic/sedative medication's prescribed daily dose divided by the sum of the minimum effective dose (as estimated by the FDA minimum recommended dose) and the patient's daily dose. The DBI includes over-the-counter medications. We will calculate the DBI at baseline and all follow-up timepoints. Importantly, the DBI captures reductions in dose, even when total number of medications is not reduced.

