### **Secondary Outcomes – Quality of Life, Safety, and Feasibility**

Dementia Quality of Life Instrument – Proxy Version (DEMQOL- Proxy): The DEMQOL-Proxy scale is used to evaluate health-related quality of life in participants with severe dementia as rated by their caregivers. It is a 31-item version (DEMQOL-proxy, rated by the caregiver). Both versions are recommended for evaluating participants (and their caregivers) with mild to moderate dementia. The DEMQOL total score ranges from 28 to 112. The DEMQOL-proxy has 31-items which are reported on a four-point Liker scale (a lot/quite a bit/a little/not at all) with a total score range from 31 to 124. Higher scores indicate a better health-related quality of life.

Behavioral & Psychological Symptoms of Dementia (BPSD): The total number of BPSD episodes recorded. The following portions of the medical chart should be requested for review: nurses notes and incident reports. To tally the total number, the reviewer (KSP) should highlight each individual episode that requires intervention or redirection from staff, or accounts for declining care (such as refusing a shower). Documented episodes may mention physical or verbal aggression or agitation, episodes of wandering into others' rooms, or off the unit, episodes of packing up belongings or taking items belonging to others.

Falls: Falls are highly prevalent in this population and lead to fatal and non-fatal injuries. To determine the total number of falls, the following portions of the medical chart should be requested for review: Nursing notes, incident reports, monthly falls report. KSP should compare each event's source with other sources to avoid double-counting falls.

Unplanned Healthcare Utilizations: Request incident reports and nursing notes of all residents who visited the emergency department or had a hospitalization. All documented emergency department visits and hospitalizations need to be tallied and recorded on the chart abstraction data sheet.

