## **STUDY INTERVENTION**

Our deprescribing protocol is based on a conceptual framework by Holmes that considers patient and disease factors, goals of care, appropriate treatment targets, and the duration of treatment required for benefit (Figure 2). We also incorporated medication-specific factors from Scott's framework for minimizing inappropriate medication use, such as drug-specific safety profiles and drug-drug and drug-disease interactions. Finally, patient preferences were viewed as a key component that informs final deprescribing actions by identifying medications the patient is willing to deprescribe (e.g., due to lack of efficacy, poor compliance, side effects, or cost burden) as well as potential barriers to deprescribing (e.g., concerns about worsening of symptoms). Specifically, our goal was to identify opportunities for deprescribing wherein clinical evidence aligned with patient preferences.

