**Table 2. Deprescribing Rationale**

A. No indication for medication / Indication not clear	F. High risk medication based on: 
 
1. Potential drug-drug interaction
 
2. Potential drug-disease interaction
 
3. On explicit PIMs list (i.e., Beer's, STOPP, or RASP)
 

B. Wrong dose or directions for medication	G. Medications are inconsistent with goals of care
C. Inappropriate for current indication due to: 
 
1. Indication has resolved
 
2. Patient is below treatment threshold
 
3. Treating guidelines have changed, medication no longer indicated
 
4. Wrong Indication for medication
 
	H. Risk > benefit given patients limited life expectancy
D. Medication is ineffective as evidenced by no change in symptom or condition	I. Evidence of poor adherence or high risk of poor adherence (directions impractical, high cost)
E. Duplicate medication for same indication	J. Medication currently indicated, however is time-limited and expect indication to resolve

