## Incorporate Resident/Surrogate Preferences

Following identification of medications for potential deprescribing, residents/surrogates will have a semi-structured interview by the study NP to elicit their preferences regarding medications identified for deprescribing (see “Deprescribing Conversation Guide” supplement). The following will be assessed for each targeted medication: medication adherence, side effects, perceived benefit/harm of the medication, cost, and level of interest in stopping or reducing the medication on a scale of 1 to 10. As part of this interview the NP may need to provide education about individual medications (e.g., side effects, risk-benefit, current evidence) and address any questions or concerns before asking if the surrogate agrees to deprescribe. If the surrogate raises a concern about a medication which the study team did not target for deprescribing, the NP should still address these concerns and note them in communications with the ALF medical team.

Study clinicians take field notes during the interview in which they detail the surrogate's general comments about medications and prescribers as well as the rationale for the agreement/disagreement with each deprescribing recommendation. After the interview these comments are coded into pre-set barriers and enablers (e.g., appropriateness, fear, process, influences, pragmatic, and dislike) from an established framework. Surrogate comments can align with more than one category for each medication and should be coded as such. A second study team member, usually the data manager, independently reviews the interview comments and coded for agreement. If there is disagreement related to categorization, the team discuss the theme assignment until a consensus is reached.

[figure not shown]

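### The BPSD count can include medication refusals, which deprescribing may reduce without any change in behaviour; tally them separately and analyse Aim 3a without and with them

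*Combined protocol and SAP*

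**What the plan says.** Secondary Outcomes – Quality of Life, Safety, and Feasibility defines BPSD as the total number of recorded episodes. The reviewer is to "highlight each individual episode that requires intervention or redirection from staff, or accounts for declining care (such as refusing a shower"). The listed examples are aggression, agitation, wandering, packing up, and taking others' items. Medication refusal is neither included nor excluded. On sources the section says: "The following portions of the medical chart should be requested for review: nurses notes and incident reports". The medication administration record is named elsewhere, for the medication count: "The primary data source is the resident's ALF medication administration record (MAR").

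Adherence enters the intervention in three places:
- Table 2, Deprescribing Rationale, item I: "Evidence of poor adherence or high risk of poor adherence (directions impractical, high cost").
- Study Intervention, among the reasons a patient may be willing to deprescribe: "due to lack of efficacy, poor compliance, side effects, or cost burden".
- Incorporate Resident/Surrogate Preferences: "The following will be assessed for each targeted medication: medication adherence, side effects, perceived benefit/harm of the medication, cost".

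Aim 3a in the Précis predicts no significant reduction in quality of life, "as measured by Behavioral and Psychological Symptoms of Dementia (BPSD) events" and by DEMQOL-Proxy scores, at 90 days. Under Statistical Considerations, BPSD is modelled by GEE with two-sided tests at 0.05. Each resident's three-month retrospective review serves as the control. No margin is given.

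**The concern.** The outcome meant to show behavioural harm may contain a component that the intervention itself can lower. A stopped drug can no longer be refused. If a resident's refusals of that drug had been tallied as declined care, those episodes leave the count whether or not behaviour has changed.

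That movement is in the direction Aim 3a hopes for. A real rise in agitation or aggression after withdrawal could be partly offset by the lost refusals, and a non-significant difference would then be taken as support. The comparison is with the resident's own earlier period, so no concurrent arm would expose the offset. The Limitations paragraph mentions time-related threats and carryover, but not overlap between the outcome definition and the intervention.

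BPSD carries much of Aim 3a. In Table 1 it is the only quality-of-life measure with a retrospective period and 30- and 60-day readings. The estimates are also meant to inform the later multi-center trial.

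**Working it through.** The plan gives no BPSD rate, refusal rate, effect size or margin, so there is no stated figure to reproduce. What follows is a bias identity with assumed inputs.

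**Inputs**
- f, the share of tallied episodes that are medication refusals: assumed 0–40%. Zero is included because the text allows it.
- r, the share of those refusals that disappear after deprescribing: assumed 25–50%. For scale, the Study Setting section gives a mean of 7.78 medications at the first facility. If 2 drugs were stopped (assumed) and refusals were spread evenly over drugs, r = 2/7.78 = 25.7%. The 50% value stands for refused drugs being stopped more often than others.

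**Formulas**
- Change in the total with no change in behaviour: −f × r.
- True rise in all other BPSD that would be exactly hidden: f × r / (1 − f).

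| f | r | Change in total | Rise in other BPSD fully hidden |
|---|---|---|---|
| 0% | any | 0% | 0% |
| 10% | 25% | −2.5% | 2.8% |
| 10% | 50% | −5.0% | 5.6% |
| 20% | 25% | −5.0% | 6.25% |
| 20% | 50% | −10.0% | 12.5% |
| 40% | 25% | −10.0% | 16.7% |
| 40% | 50% | −20.0% | 33.3% |

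**Worked case.** Take f = 30% and a true 15% rise in all other episodes. The observed ratio is (1 − f) × 1.15 + f × (1 − r).
- r = 25.7%: 0.805 + 0.223 = 1.028, seen as +2.8%.
- r = 50%: 0.805 + 0.150 = 0.955, seen as −4.5%.

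**Effect on the test, for illustration only.** Enrollment of 40 with 10% attrition leaves 36. Assume a within-subject SD of the log ratio of 0.8 and a true 25% rise in other BPSD. Approximate power is Φ(|ln ratio| × √n / SD − 1.96).
- No refusals in the count: ratio 1.25, 0.223 × 6 / 0.8 = 1.67, power about 39%.
- f = 20%, r = 25%: ratio 0.8 × 1.25 + 0.2 × 0.75 = 1.15, 0.140 × 6 / 0.8 = 1.05, power about 18%.

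With refusals out of the tally, f = 0 and the artefact is zero whatever r is.

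**The case against.** A reader might infer that the BPSD count must fall by construction and that Aim 3a is therefore biased toward no worsening. The documents do not support that, for several reasons.

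- The BPSD rule never mentions medication. The administration record is not a BPSD source, so a refusal recorded only there is not tallied.
- Poor adherence is one of ten rationales, and its parenthetical concerns impractical directions and cost. Priority is set by potential harm and effects on geriatric syndromes. Surrogate and provider must both agree, and the action may be only a dose reduction, which need not remove an administration.
- The rule counts episodes, not pills. A resident who refuses a whole medication pass may produce one episode however many drugs are offered, in which case r could be zero.
- The net direction is not settled. Several deprescribing actions call for symptom monitoring, and weekly follow-up is described under the approach to risks. Closer observation could raise the number of charted episodes.
- Some lost refusals may be a real benefit, if stopping an unwanted drug ends repeated conflict over care. Some refusals are genuine resistive behaviour.
- DEMQOL-Proxy, the other Aim 3a measure, is untouched by this route.
- This is a pilot with no formal power analysis, and the illustration gives only about 39% power even without the artefact. Reading non-significance without a margin as no worsening is a separate and larger weakness.

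All of these stand as limits on size and certainty. They do not close the gap: the category of declined care is open-ended, nothing excludes charted medication refusals, and two abstractors could reasonably differ on them.

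**Conclusion.** The narrower point holds. The BPSD rule can take in medication refusals charted in nurses' notes or incident reports. The intervention reduces the number of drugs offered and names poor adherence as one reason to act. If refusals are counted and some disappear with the drugs, that component pushes the total down and could partly mask a rise in other BPSD.

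The size cannot be fixed from the documents and may be nil. Over the assumed ranges (refusals 0–40% of the tally, 25–50% of them removed) the total falls by 0–20%, enough at the upper end to hide a 33.3% rise in other episodes. The documents do not show that refused drugs are preferentially stopped, that the whole count falls, or that the net bias runs one way. The clarification is worth making because it is cheap and removes an overlap that would favour the study's hypothesis.

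**What to change.** In the BPSD paragraph of Secondary Outcomes:
- State that medication refusals are tallied on a separate line, from the same sources (nurses' notes and incident reports) in the retrospective and follow-up periods.
- Run the Aim 3a BPSD analysis both without and with medication refusals, and state in advance which is the main total.
- Claim no worsening only if the total without medication refusals also supports it.

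Which total should be the main one is a judgement. Leaving refusals out removes the overlap but also drops some real resistive behaviour, so both should be reported.

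The cost is one extra line on the abstraction form, completed from notes already requested. Data already collected can be re-abstracted from the same notes. The downside is that refusals which are genuine behavioural symptoms appear only in the inclusive total. The change does not address the missing margin in Aim 3a.

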## **STUDY INTERVENTION**

Our deprescribing protocol is based on a conceptual framework by Holmes that considers patient and disease factors, goals of care, appropriate treatment targets, and the duration of treatment required for benefit (Figure 2). We also incorporated medication-specific factors from Scott's framework for minimizing inappropriate medication use, such as drug-specific safety profiles and drug-drug and drug-disease interactions. Finally, patient preferences were viewed as a key component that informs final deprescribing actions by identifying medications the patient is willing to deprescribe (e.g., due to lack of efficacy, poor compliance, side effects, or cost burden) as well as potential barriers to deprescribing (e.g., concerns about worsening of symptoms). Specifically, our goal was to identify opportunities for deprescribing wherein clinical evidence aligned with patient preferences.

## Conceptual Model

**Figure 2. Deprescribing Framework**

As shown in Figure 1, the study has three stages with intervention occurring in Stages 2 & 3. Each step is described in detail below, and Figure 3 shows the order of the intervention.

### Pre-Review (Target Medications for Deprescribing)

Using medical record data only, a study NP will gather the following information for each medication: (1) Medication – Indication pairing: For each medication, an indication (i.e., diagnosis or symptom) will be identified. If an indication does not exist, “no indication indicated” will be specified; and, (2) De-prescribing rationale: Each medication will be assessed for the potential rationales for deprescribing shown in Table 2, indicating all applicable rationales.

All medications, both prescription and OTC including vitamins and herbal supplements, are reviewed for potential deprescribing. Select medication classes will not be under consideration for active deprescribing, which include the following:

- Anti-rejection medications for organ/ bone-marrow transplantation
- Chemotherapeutic medications for the treatment of known solid organ or hematologic malignancy.

The above medications may be deprescribed during the study period; however, it would solely be under the direction of the primary prescriber of the medication.

Deprescribing Priority: Although any rationale may be appropriate for deprescribing medications, a study NP will establish a priority level of 1 (low) to 10 (high) for discussing deprescribing recommendations. Priority will consider potential harm of the medication and potential effects on geriatric syndromes. It may be inappropriate to deprescribe multiple medications simultaneously; thus, prioritization may guide the surrogate interview and the deprescribing order.

**Deprescribing Action Recommendations:** For any medications recommended for deprescribing, the study NP will recommend a deprescribing action: (1) Stop now without need for monitoring; (2) Stop with symptoms/physiologic monitoring; (3) Stop at specified time point; (4) Reduce over time with monitoring until medication is stopped; (5) Reduce to lower dose without need for monitoring; (6) Reduce to lower dose with symptoms /physiologic monitoring. All recommendations will be discussed with primary prescribers (**Step 2b**) and surrogate decision-makers (**2c**).

**Table 2. Deprescribing Rationale**

A. No indication for medication / Indication not clear	F. High risk medication based on: 
 
1. Potential drug-drug interaction
 
2. Potential drug-disease interaction
 
3. On explicit PIMs list (i.e., Beer's, STOPP, or RASP)
 

B. Wrong dose or directions for medication	G. Medications are inconsistent with goals of care
C. Inappropriate for current indication due to: 
 
1. Indication has resolved
 
2. Patient is below treatment threshold
 
3. Treating guidelines have changed, medication no longer indicated
 
4. Wrong Indication for medication
 
	H. Risk > benefit given patients limited life expectancy
D. Medication is ineffective as evidenced by no change in symptom or condition	I. Evidence of poor adherence or high risk of poor adherence (directions impractical, high cost)
E. Duplicate medication for same indication	J. Medication currently indicated, however is time-limited and expect indication to resolve

## Incorporate Resident/Surrogate Preferences

Following identification of medications for potential deprescribing, residents/surrogates will have a semi-structured interview by the study NP to elicit their preferences regarding medications identified for deprescribing (see “Deprescribing Conversation Guide” supplement). The following will be assessed for each targeted medication: medication adherence, side effects, perceived benefit/harm of the medication, cost, and level of interest in stopping or reducing the medication on a scale of 1 to 10. As part of this interview the NP may need to provide education about individual medications (e.g., side effects, risk-benefit, current evidence) and address any questions or concerns before asking if the surrogate agrees to deprescribe. If the surrogate raises a concern about a medication which the study team did not target for deprescribing, the NP should still address these concerns and note them in communications with the ALF medical team.

Study clinicians take field notes during the interview in which they detail the surrogate's general comments about medications and prescribers as well as the rationale for the agreement/disagreement with each deprescribing recommendation. After the interview these comments are coded into pre-set barriers and enablers (e.g., appropriateness, fear, process, influences, pragmatic, and dislike) from an established framework. Surrogate comments can align with more than one category for each medication and should be coded as such. A second study team member, usually the data manager, independently reviews the interview comments and coded for agreement. If there is disagreement related to categorization, the team discuss the theme assignment until a consensus is reached.

[figure not shown]
### Outpatient & ALF Provider Input

The study NP will serve as a centralized source of communication. The study NP will notify the facility NP/MD of resident enrollment and will review and discuss all deprescribing recommendations to ensure they do not conflict with ongoing care. Following the resident/surrogate interview, the study NP will contact the primary prescriber for agreed upon medications, this could be the ALF provider, an outpatient specialist, or both. The goal of these conversations is to obtain provider feedback about the proposed changes and facilitate medication updates in the medical record. Additionally, these conversations will hopefully lead to sustained deprescribing by engaging the primary provider early in the process.

Much like the patient preference interview, the study NP documents the original prescriber's agreement/disagreement and rationale for their decision. These field notes are coded into pre-set barrier and enabler categories (e.g., inertia, self-efficacy, feasibility) from a published framework.

### Final Deprescribing Actions

The final step in the intervention is to review the final list of medications all parties (surrogate and provider) agreed to deprescribe with the ALF NP/MD and have them update the medication orders in the ALF EMR.

## SAFETY MONITORING AND ASSESSMENTS

We have established a system to report and track adverse events (AEs) including adverse drug withdrawal events (ADWEs), serious adverse events (SAEs), and Suspected Unexpected Serious Adverse Reaction (SUSARs). In this study, an SAE is defined as an unplanned hospitalization or death, and an AE is defined as an emergency room visit that does not result in hospitalization. A SUSAR is an SAE that is suspected to be secondary to the drug withdrawal and is unexpected. Study personnel will monitor the safety of subjects and follow them until the event resolves or is explained.

